**Has been changed to read:**

Conventional CT with contrast should be performed with cuts of 5 mm or less in slice thickness contiguously. This applies to tumors of the chest and abdomen. A scale should be incorporated into all radiographic measurements. MRI can be performed if required by local law, but should have sponsor approval.

[figure not shown]
If prior to enrollment, it is known that a subject is not able to undergo CT scans with IV contrast due to allergy or renal insufficiency, the decision as to whether a non-contrast CT or MRI should be used to evaluate the subject at baseline and follow-up should be made. This decision should be guided by the tumor type under investigation and the anatomic location of the disease and the outcome of the decision should be communicated to AbbVie.

### **3.0 Introduction**

Veliparib is a novel small molecule and also a potent oral PARP inhibitor that delays the repair of DNA damage induced by chemotherapeutic agents, including alkylating/methylation agents (TMZ, cyclophosphamide), crosslinking agents (cisplatin, carboplatin), platinum agents, topoisomerase inhibitors (irinotecan), and radiation. Nonclinical efficacy with veliparib in combination with these agents has been demonstrated across an array of tumor types, including melanoma, glioma, prostate, breast, and colon.

Preclinical studies data suggest the addition of veliparib to carboplatin would enhance the efficacy of carboplatin in several xenograft tumor models. In the BRCA1 deficient MX-1 model, veliparib administered at doses as low as 25 mg/kg/day significantly enhanced the efficacy of carboplatin. On the other hand, etoposide in combination with other approved chemotherapeutic agents is FDA approved as first-line treatment in subjects with SCLC. Carboplatin in combination with etoposide (both IV and oral formulations) has been extensively tested in randomized clinical trials in SCLC as well as in other tumor types.

Therefore, this study (Study M14-361) is being conducted to assess efficacy and toxicity of veliparib versus placebo in combination with carboplatin and etoposide in the treatment of subjects with ED SCLC who are previously untreated.

This SAP provides details to further elaborate statistical methods as outlined in Clinical Study Protocol M14-359 incorporating Amendments 1, 2, 3 and 4, and describes analysis conventions to guide the statistical programming. Analyses will be performed using SAS® Version 9.3 (SAS Institute, Inc., Cary, NC) or later under the UNIX operating system.

## **4.0 Study Objectives, Design and Procedures**

### **4.1 Objectives**

The primary objective of the study is to evaluate if the addition of veliparib in combination with carboplatin and etoposide followed by veliparib maintenance monotherapy results in improved progression free survival (PFS) versus placebo in combination with carboplatin and etoposide followed by placebo monotherapy in subjects with treatment-naïve ED SCLC.

The secondary objectives of the study are to evaluate (1) if veliparib in combination with carboplatin and etoposide followed by placebo monotherapy results in improved PFS versus placebo in combination with carboplatin and etoposide followed by placebo monotherapy in subjects with treatment-naïve ED SCLC; (2) if veliparib in combination with carboplatin and etoposide results in improved objective response rate (ORR) versus placebo in combination with carboplatin and etoposide, at the time of completion of maintenance therapy, or completion of combination therapy if subject was not involved in maintenance phase. In protocol v.5 dated 22 NOV 2016, Chapter 4.0, objective response rate is to be evaluated by the combination therapy for all subjects. We modified the analysis period by adding maintenance phase following ITT (intent-to-treat) population principle to avoid observation bias; (3) if veliparib in combination with carboplatin and etoposide followed by veliparib maintenance monotherapy results in improved overall survival (OS) versus placebo in combination with carboplatin and etoposide followed by placebo monotherapy; (4) if veliparib in combination with carboplatin and etoposide followed by placebo monotherapy results in improved OS versus placebo in combination with carboplatin and etoposide followed by placebo monotherapy; (5) to further evaluate the safety of veliparib in combination with carboplatin and etoposide followed by veliparib maintenance monotherapy.

The tertiary objectives are to (1) evaluate if veliparib in combination with carboplatin and etoposide followed by veliparib maintenance monotherapy results in improved duration of overall response (DOR) versus placebo in combination with carboplatin and etoposide

followed by placebo monotherapy; (2) evaluate if veliparib in combination with carboplatin and etoposide followed by placebo monotherapy results in improved DOR versus placebo in combination with carboplatin and etoposide followed by placebo monotherapy; (3) compare PFS and OS of subjects treated with veliparib in combination with carboplatin and etoposide followed by veliparib maintenance to PFS and OS of subjects treated with veliparib in combination with carboplatin and etoposide followed by placebo maintenance; (4) evaluate ECOG performance status.

## **4.2 Design Diagram**

This is a Phase 1 dose escalation and Phase 2 randomized double-blind study of veliparib in combination with carboplatin and etoposide and maintenance veliparib monotherapy. The veliparib dose and schedule for the Phase 2 was determined to be 240 mg BID (twice a day) on a 14-day schedule for up to 6 cycles (21 days per cycle) based on the analysis of Phase 1 data. This SAP is only for Phase II part of the study. Analysis for Phase I part will be presented in CSR Phase I portion and when the study is complete PK analysis will be drafted in Appendix 16.1\_\_9.1.

Approximately 180 adult male or female subjects with treatment-naïve ED SCLC will be selected to participate in the study to meet scientific and regulatory objectives without enrolling an undue number of subjects in alignment with ethical considerations. Subjects will be randomized in a 1:1:1 ratio to one of three treatment arms:

Arm A: veliparib 240 mg BID in combination with carboplatin/etoposide for up to 6 cycles followed by veliparib 400 mg BID monotherapy;

Arm B: veliparib 240 mg BID in combination with carboplatin/etoposide for up to 6 cycles followed by placebo monotherapy;

Arm C: placebo in combination with carboplatin/etoposide for up to 6 cycles followed by placebo monotherapy;

Subject randomization for Phase 2 will be stratified by gender and baseline lactate dehydrogenase (LDH) level, that is, > Upper Limit of Normal (ULN) versus  $\leq$  ULN. The stratification factors used for the randomization should be the last values on or prior to the date of randomization and should be consistent with those on the eCRF.

The detailed dosing schedules for these three groups of the study are presented below in [Table 1](#).

**Table 1. Treatment Schema for Combination Cycles in Phase 2**

Days	-2	-1	1	2	3	4 - 12
Veliparib/Placebo	240 mg BID	240 mg BID	240 mg BID	240 mg BID	240 mg BID	240 mg BID
Carboplatin			Once			
Etoposide			Once	Once	Once	

Subjects in all Phase 2 study arms will receive a minimum of 4 cycles of combination therapy unless disease progression or unacceptable toxicity warrants earlier discontinuation from the treatment. Additional 2 cycles of combination therapy (e.g., up to a total of 6 cycles) may be administered at the investigators discretion if subject status at the completion of initial 4 cycles warrants continued combination treatment and/or if local SOC guidelines require 6 cycles of platinum-based therapy. Subjects enrolled in these additional 2 cycles of combination therapy will receive veliparib at 400 mg BID continuous dosing (21-day cycles) (Arms A), or matching placebo (Arms B and C) as per treatment arm assignment, until disease progression (PD) or unacceptable adverse events (AEs) occur.

All subjects will remain on study until reaching a protocol-defined event of PD or AE due to veliparib or carboplatin/etoposide. Otherwise, appropriate dose modifications or dosing delays should be managed according to protocol. Subsequent cycles of therapy will be administered if there is no evidence of PD and observed toxicities have recovered adequately as described in protocol.

### **4.3 Sample Size**

Assuming a median PFS of 5.5 months for placebo in combination with carboplatin and etoposide followed by placebo monotherapy (Arm C) and a hazard ratio of 0.63 for veliparib in combination with carboplatin and etoposide followed by veliparib monotherapy (Arm A) versus Arm C, a total of 85 PFS events will provide an least 80% power to detect a statistically significant difference between Arm A and Arm C at a one-sided  $\alpha = 0.1$ .

Further assuming a hazard ratio of 0.75 for veliparib in combination with carboplatin and etoposide followed by placebo monotherapy (Arm B) versus Arm C, a total of 126 PFS events will be observed across all three arms at the time when 85 PFS events are observed for Arm A and Arm C combined. A total of approximately 180 subjects (60 subjects per treatment arm) will be enrolled into the study to obtain the 126 PFS events.

### **4.4 Interim Analysis**

A safety DMC (Data Monitoring Committee) was set up for the Phase 2 portion of the study to review the aggregate unblinded safety data. The initial safety DMC review will occur once at least 30 Phase 2 subjects have met criterion 1) and 2), or 3), or 4).

- 1). Received at least one dose of veliparib/placebo;
- 2). Started Cycle 5; or
- 3). Discontinued (not death) prior to Cycle 5 due to AE not related disease progression; or
- 4). Death prior to Cycle 5 not due to disease progression.

Data cutoff date was Aug. 25th, 2017 and the safety DMC meeting was held on Oct. 18th, 2017. Based on this initial safety DMC review, it's decided that it's not necessary to have another safety review before DB lock. The details of the safety DMC setup and procedure was outlined in Appendix [14.1.7](#).

## **5.0 Analysis Populations**

### **5.1 Definition for Analysis Population**

Two study populations will be analyzed, respectively defined as follows:

Intent-To-Treat (ITT) population – all subjects who were randomized using an IRT (interactive response technology) system. The data from ITT population will be analyzed by the treatment group assignment given at the time of randomization, even if the subject takes the incorrect drugs that do not match the assigned treatment, or does not receive any treatment, or does not follow the protocol until completion.

As-Treated (AST) population – all subjects who were randomized by IRT system and took at least 1 dose of study drug (veliparib/placebo). The data from AST population will be analyzed by the actual treatment that subject received.

### **5.2 Variables Used for Stratification of Randomization**

Subject randomization were stratified by LDH level ( $> ULN$  versus  $\leq ULN$ ), and gender (female versus male).

## **6.0 Analysis Conventions**

Unless otherwise noted, for all statistical analyses, statistical significance will be determined by a one-sided P value  $\leq 0.1$  (when rounded to one decimal place). The date of randomization is defined as the date that the IRT issued a subject number.

Unless otherwise specified, demographic and baseline characteristics, medical history, prior oncological therapies, and other medications, as well as all efficacy analyses will be performed on Phase 2 ITT population, and all safety analyses will be performed on Phase 2 AST population. Summary data will be presented for each of the three treatment arms (A, B, C), or as indicated otherwise.

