### **Phase 2 Randomized Double-Blind**

Assuming a median PFS of 5.5 months for placebo in combination with carboplatin and etoposide followed by placebo monotherapy (Arm C) and a hazard ratio of 0.63 for veliparib in combination with carboplatin and etoposide followed by veliparib monotherapy (Arm A) versus Arm C, a total of 85 PFS events will provide an least 80% power to detect a statistically significant difference between Arm A and Arm C at a one-sided  $\alpha = 0.1$ . Further assuming a hazard ratio of 0.75 for veliparib in combination with carboplatin and etoposide followed by placebo monotherapy (Arm B) versus Arm C, a total of 126 PFS events will be observed across all three arms at the time when 85 PFS events are observed for Arm A and Arm C combined. A total of approximately 180 subjects (60 subjects per treatment arm) will be enrolled into the study to obtain the 126 PFS events.

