## **10.0 Efficacy Analysis**

### **10.1 General considerations**

Unless otherwise noted, for all statistical analyses, statistical significance will be determined by a one-sided P value  $\leq 0.1$  (when rounded to two decimal places). Confidence intervals will be two-sided 80% for all descriptive statistics. The date of randomization is defined as the date that the IRT issued a subject number.

The efficacy analyses will be performed on Phase 2 ITT population and presented by treatment arm. All randomized subjects will be included unless otherwise specified. The dosing schedules for each of the three arms are listed in detail in Section 4.2.

After observing 95 PFS events (75% of 126), a model-based prediction was performed to estimate the approximate date of the 126th PFS events across all 3 arms. The prediction estimated Sep. 14th, 2018 as the date of 126 PFS events across the three arms. Unless otherwise specified, Sep. 14th, 2018 will be the cutoff date for all efficacy analyses.

For all efficacy endpoints except OS, if a subject's blind has prematurely broken by sites before cutoff date, the date of premature blind break will be set as the cutoff date for that subject.

If a subject starts any systemic anti-cancer therapy post-discontinuation of study therapy, then PFS and DOR will be censored at last non-missing tumor assessment prior to the initiation date of the new systemic anti-cancer therapy; similarly ORR/DOR will be based only on tumor assessment prior to the initiation of any new systemic anti-cancer therapy.

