## 10.2 Testing Hierarchy

This is a single primary efficacy endpoint (PFS, Arm A vs Arm C) study. Survival data (a total of approximately 136 death events targeted across all three treatment arms) will not be mature at the PFS primary analysis time, thus OS analysis at the time of PFS primary analysis will be considered as an interim analysis. If statistical test is significant (one-sided P value  $\leq 0.1$ ) for the primary efficacy endpoint, then the fixed sequence testing procedure will be performed with a significance level of 0.1 (one-sided) for key secondary efficacy endpoints sequentially. If primary PFS (Arm A vs. Arm C) is not significant, then statistical significance will not be declared for any of the secondary efficacy endpoints.

Hierarchical ranking and alpha spending for primary and each secondary endpoint at the time of PFS primary analysis and OS primary analysis is presented in [Table 5](#).

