**Table 5. Alpha-spending Boundary (One-sided p-value) for Each Ranked Endpoint**

Endpoint	Timing	
	PFS Primary Analysis (approximately 126 PFS events across all 3 arms)	OS Primary Analysis (approximately 136 deaths across all 3 arms)
PFS (A vs C)	0.1	NA
OS (A vs C)	0.0001 (administrative purpose)	0.1
PFS (B vs C)*	0.1	
OS (B vs C)	0.0001 (administrative purpose)	0.1
ORR (A vs C)*	0.1	
ORR (B vs C)*	0.1	

(A, B, and C correspond to the three treatment arms, respectively.)

\* Analysis sets for these three tests are the same as PFS (A vs C).

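### SAP 6.0 and 10.1 round the one-sided P value differently before comparing it with 0.1, and both clauses are looser than the 0.10 the trial was sized for

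*SAP*

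**What the plan says.** SAP 6.0 (Analysis Conventions) and SAP 10.1 (General considerations for efficacy) carry the same sentence. In 10.1 it reads that, unless noted otherwise, "for all statistical analyses, statistical significance will be determined by a one-sided P value" of at most 0.1. The two sentences differ only in the parenthesis that follows: "when rounded to one decimal place" in 6.0, "when rounded to two decimal places" in 10.1.

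Four other places give the level with no rounding clause:

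- SAP 4.3 sizes the trial "to detect a statistically significant difference between Arm A and Arm C at a one-sided" level of 0.1.
- Protocol 8.2 has the same calculation: "a total of 85 PFS events will provide an least 80% power" at that level.
- SAP 10.2 first asks for a one-sided P of at most 0.1 on PFS for Arm A against Arm C. Once that is met, "then the fixed sequence testing procedure will be performed with a significance level of 0.1 (one-sided) for key secondary efficacy endpoints sequentially". When that comparison fails, "statistical significance will not be declared for any of the secondary efficacy endpoints".
- SAP Table 5, titled "Alpha-spending Boundary (One-sided p-value) for Each Ranked Endpoint", lists 0.1 for PFS (A vs C).

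SAP 10.1 also sets confidence intervals at two-sided 80%, which is the counterpart of an unrounded one-sided 0.10.

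**The concern.** Rounding before comparing changes the cut-off. A P value of 0.104 becomes 0.10 at two decimals and passes; a P value of 0.12 becomes 0.1 at one decimal and passes. Neither passes against a plain 0.1. So the SAP contains three possible thresholds for the same test, and two of them exceed the level behind the sample size.

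Primary PFS is the gate to the whole hierarchy, so a near-miss there would also settle whether PFS (B vs C), ORR and OS can be declared significant. With a P value between 0.100 and 0.105, one analyst could cite 10.1 and claim success, and another could cite 10.2 and Table 5 and report failure. The first verdict could also stand beside an 80% interval for the hazard ratio that includes 1. A choice of this kind should not remain open once the blind is broken.

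**Working it through.** **Inputs.** Hazard ratio 0.63 for Arm A versus Arm C, 85 PFS events in those two arms, at least 80% power, one-sided 0.1 (SAP 4.3, Protocol 8.2). Randomization is 1:1:1, hence 1:1 for A versus C (SAP 4.2). The Schoenfeld approximation is my choice, as the documents name no formula.

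**Cut-offs in effect.** One decimal: P rounds to 0.1 or less if it is below 0.15. Two decimals: P rounds to 0.10 or less if it is below 0.105. How exact halves are rounded does not matter here.

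**Formulas**, with z the upper-tail normal quantile of the level:

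- Events for 80% power = 4(z + 0.8416)² / (ln 0.63)², with (ln 0.63)² = 0.2135
- Power with 85 events = Φ(−ln 0.63 × √85 / 2 − z) = Φ(2.1299 − z)
- Critical hazard ratio = exp(−2z / √85)

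**The plan's own figure.** At 0.10, z = 1.2816, so events = 4 × (2.1232)² / 0.2135 = 84.47, rounded up to 85. This matches the plan. Power is Φ(0.8483) = 80.2%.

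**The three thresholds**

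| Rule | Level | z | Critical HR, 85 events | Power, 85 events | Events for 80% power |
|---|---|---|---|---|---|
| Unrounded (4.3, 10.2, Table 5, Protocol 8.2) | 0.10 | 1.2816 | 0.757 | 80.2% | 84.47 → 85 |
| Two decimals (10.1) | 0.105 | 1.2536 | 0.762 | 81.0% | 82.25 → 83 |
| One decimal (6.0) | 0.15 | 1.0364 | 0.799 | 86.3% | 66.09 → 67 |

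**Chance of the disputed window, 0.100 to 0.105.** Under the null: 0.105 − 0.100 = 0.005, or 0.5%. At a hazard ratio of 0.63: 0.8096 − 0.8019 = 0.0077, or about 0.8%.

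**The case against.** The strongest reply is that the SAP already settles the matter. Both general sentences allow for exceptions, and 10.2 and Table 5 then give a specific rule for primary PFS, 0.1 with no rounding. Read specific over general, the operative level is 0.10 and the clauses do nothing. This reading is reasonable, but the text does not compel it. Section 10.2 repeats the 0.1 threshold without disclaiming the rounding that 10.1, the general convention for the same efficacy tests, attaches to that very threshold. Both readings can be defended.

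Other points have some force:

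- **The 6.0 clause has little to act on.** The SAP plans no statistical comparison for baseline data, medical history or prior therapy, and none for safety unless specified. The tests that matter sit under Section 10. This stands, and it is why 0.15 is reported only as an outer bound.
- **The event count does not by itself identify the level.** Power is claimed as at least 80%, which 85 events also satisfy at 0.105, and Freedman's formula gives 88 events at 0.10. This stands too. The level is known because the documents state it; the 85 events agree with it under Schoenfeld.
- **Table 5's 0.0001 interim OS boundary is equally silent on rounding.** For that reason no inflation is claimed for OS.
- **The efficacy tests are described as two-sided while significance is one-sided.** The derivation of the one-sided P could usefully be stated, but that is a separate detail.
- **The window is very narrow.** True, and it limits the severity, but it does not remove the contradiction.

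**Conclusion.** The concern holds. The two clauses contradict each other, and each sets a cut-off above the one-sided 0.10 used for the design. The practical effect on primary PFS is a level of about 0.105 if 10.1 is applied as written: 0.5 points more type I error and about 0.8 points more power (80.96% against 80.19%) than under the unrounded rule. Applying 6.0 would take the level to about 0.15, but the more specific efficacy sections make that unlikely.

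This should be fixed, although it does not threaten the design. The reason to act is that a decision threshold gating every ranked secondary test should have one value before unblinding. The figures assume Schoenfeld's approximation, 1:1 allocation between Arms A and C, proportional hazards at 0.63 and exactly 85 events in those arms. The contradiction itself rests on the wording alone.

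**What to change.** Delete both rounding clauses and put the same sentence in SAP 6.0 and SAP 10.1, for example:

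> *Subject to the fixed sequence in Section 10.2, a ranked endpoint is significant if its unrounded one-sided P value is at most its Table 5 boundary; any other test uses an unrounded one-sided P of at most 0.10. P values are rounded for display only.*

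Naming the Table 5 boundaries also makes clear that no rounding applies to the interim OS boundary.

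The cost is one sentence in each section. Events, sample size and data collection do not change. If an analysis program rounds P before comparing it, that step must be removed; the documents do not show the programs. The only loss is the extra 0.8 points of power under the 10.1 rule, which the design never claimed.

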### **Definition of Study Drug**

Unless otherwise specified, the study drug in this document refers to veliparib/placebo, and carboplatin/etoposide. The first dose date of study drug for combination period is defined as the date of the 1st dose of veliparib/placebo or carboplatin/etoposide received during combination period, whichever occurs first. The last dose date of study drug for combination period is defined as the date of the last dose of veliparib/placebo or carboplatin/etoposide received during combination period, whichever occurs later. The first dose date of study drug for maintenance period is defined as the date of the 1st dose of veliparib/placebo received during maintenance period. The last dose date of study drug for maintenance period is defined as the date of the last dose of veliparib/placebo received during maintenance period.

### **Definition of Post-Treatment Therapy**

Unless otherwise specified, the post-treatment therapy (excluding surgical and radiation therapy) in this document refers to the therapy after the last dose of study drug.

